### 12.7.2 Dose Modifications

It is unknown whether subjects in the 25 mcg and 50 mcg cohorts from the main study have been optimally primed to respond to the third mRNA-1273 vaccination. In the event that the responses to a third mRNA-1273 vaccination in either or both of those cohorts are judged to be suboptimal in comparison to the responses in the 100 mcg cohorts, the study team will inform the subjects and consider a protocol amendment to administer another mRNA-1273 vaccination at a dosage of 100 mcg.

### 12.7.3 Product Storage and Stability

#### **Product: mRNA-1273**

For the optional third mRNA-1273 vaccination substudy, mRNA-1273 must be stored in a secure area with limited access (pharmacy staff only), and must be stored locally under refrigerated conditions (2°C to 8°C [36°F to 46°F]). The refrigerator should have an automated temperature recording and alert system. There must be an available back-up refrigerator. The refrigerators must be connected to a back-up generator; or alternate plan in the event of a power failure. The pharmacy must have in place a 24-hour alert system that allows for rapid response in case of refrigerator malfunctioning.

Prepared doses should remain at ambient temperatures (20°C to 25°C) and should not be shaken or allowed to roll during transport. Avoid exposing to direct sunlight while the syringe is in route to the injection administration location. If the prepared doses require transportation to a separate facility, ensure there are appropriate transport procedures in place. Under all circumstances, the time from preparation, transportation and administration of mRNA-1273 must occur within maximum (nine) 9 hours from the time the vials are removed from the refrigerator.

- A minimum of 20 minutes and a maximum of 30 minutes are allowed for equilibration of vial to room temperature (20°C to 25°C) after removal from refrigerator.
- A maximum of 30 minutes is allowed between completion of equilibration and completion of dosing syringes fill. However, all dosing syringes (10) must be filled in quick succession once the vial is breached.

- A maximum of 8 (eight) hours is allowed for holding dosing solution in dosing syringes prior to completion of administration.
- Note that the multi-dose vial does not contain a preservative and must be discarded 6 hours after the first penetration of the sterile septum.

## 12.8 Concomitant Therapy

Information about prior medications, including hormonal contraceptives, taken by the subject in the 30 days prior to providing informed consent for the substudy will be recorded on the appropriate DCF.

Concomitant medications include all medications (prescription, over the counter, supplements, and vaccines received outside of the study) taken by the subject from the time the substudy informed consent is signed through Substudy Day 366. At each substudy visit following the third mRNA-1273 vaccination, subjects will be queried about new concomitant medications and changes to existing medications.

Medications that might interfere with the evaluation of the investigational product should not be used by the subject during the study-reporting period (12 months after the third mRNA-1273 vaccination) unless clinically indicated as part of the subject's health care.

In the event medical conditions dictate the use of medications, subjects are encouraged to obtain adequate care, comply with the course of therapy as prescribed by their physician, and inform the study Investigator as soon as practical. Any drug or vaccine used or received by the subject during the study-reporting period (12 months after the third mRNA-1273 vaccination) should be recorded on the appropriate DCF.

## 12.9 Immunogenicity Evaluations

### Serological Immunogenicity Assays:

The following serological immunogenicity assays may be performed on specimens collected on the day of and following the third mRNA-1273 vaccination:

- IgG ELISA to the SARS-CoV-2 S (spike) protein(s) and SARS-CoV-2 N protein.
- Pseudovirus and live SARS-CoV-2 neutralization assays.

### Cellular Immunology Assays:

This substudy will also investigate T cell immune responses using multiparametric flow cytometry.

The volume of venous blood to be collected at each substudy visit for immunogenicity evaluations is presented in [Table 14](#).

## 12.10 Adverse Events and Serious Adverse Events

### 12.10.1 Reporting of Adverse Events

Reporting of all AEs, solicited and unsolicited, will occur during the period from administration of the third mRNA-1273 vaccine on Substudy Day 1 through Substudy Day 29.

Solicited AEs (i.e., reactogenicity) will be collected using a memory aid and recorded on the appropriate DCF from the time of the third mRNA-1273 vaccination through 7 days post third mRNA-1273 vaccination (Substudy Days 1-8).

Unsolicited AEs of all severities will be reported from the time of the third mRNA-1273 vaccination on Substudy Day 1 through Substudy Day 29.

After Substudy Day 29 through the end of the substudy (Substudy Day 366), only SAEs, Protocol Specified AESIs, MAAEs, and NOCMCs will be reported as AEs.

SAEs, Protocol Specified AESIs, MAAEs, and NOCMCs will be collected from Substudy Day 1 through the end of the substudy (Substudy Day 366).

### **12.10.2 Reporting of Pregnancy**

Pregnancy is not an AE. However, any pregnancy that occurs during substudy participation (through Substudy Day 366 post third mRNA-1273 vaccination) should be reported to the sponsor on the appropriate DCF. Pregnancy should be followed to outcome.

### **12.10.3 Unanticipated Problem Reporting**

To satisfy the requirement for prompt reporting, UPs will be reported using the following timeline:

- UPs that are SAEs will be reported to the IRB and to the SDCC/study sponsor within 24 hours of the participating site PI or appropriate sub-investigator becoming aware of the event per the above described SAE reporting process.
- UPs that are SAEs will be collected from Substudy Day 1 through the end of the substudy (Substudy Day 366).
- Any other UP will be reported to the IRB and to the SDCC/study sponsor within 3 days of the participating site PI or appropriate sub-investigator becoming aware of the problem.
- UPs that are not SAEs will be collected from Substudy Days 1-29.

## **12.11 Statistical Considerations**

### **12.11.1 Statistical Hypotheses**

This is a substudy to a phase I, open-label, dose-ranging clinical trial and is not designed to test a specific hypothesis. Rather, it is intended to obtain preliminary estimates in healthy adults of the safety, reactogenicity, and immunogenicity of a third mRNA-1273 vaccination between 6 months and 12 months post second mRNA-1273 vaccination.

### **12.11.2 Sample Size Determination**

Rare AEs are not demonstrable in a clinical study of this size; however, the probabilities of observing one or more AEs given various true event rates are presented in [Table 9](#) and apply to the substudy as well. Statistical assumptions described in [Section 9.2](#) apply to the substudy as well. It is possible that not all subjects will receive a third mRNA-1273 vaccination, assuming 5 subjects in a cohort receive a third mRNA-1273 vaccination the chance of observing at least one

AE of probability 20% or more is approximately 67%. Assuming all subjects receive a third mRNA-1273 vaccination the following additional statistical consideration applies. With 120 subjects across all cohorts the chance of observing at least one AE of probability 3% or more is approximately 97%.

### **12.11.3 Populations for Analyses**

The Safety Analysis population includes all subjects who received the third mRNA-1273 vaccination.

The modified intent-to-treat (mITT) population includes all subjects who received of the third mRNA-1273 vaccination and contributed both pre- and at least one post-third mRNA-1273 vaccination venous blood samples for immunogenicity testing for which valid results were reported.

In the final analysis, protocol deviations will be reviewed to determine which protocol deviations may affect the analysis. The per protocol (PP) population will then be defined – and this includes all subjects in the mITT subset with the following exclusions:

- Data from all available visits for subjects found to be ineligible at the time of the third mRNA-1273 vaccination.
- Data from all substudy visits subsequent for the protocol deviations that are considered to affect the science.
- Data from any substudy visit that occurs substantially out of window.

### **12.11.4 Statistical Analyses**

Interim analyses of safety, reactogenicity, and immunologic response data may be done, as needed.

The final substudy analysis will be performed after the final data lock (through Substudy Day 366) and reported as an addendum to the clinical study report (CSR). The addendum will be completed when all primary safety endpoint data and all secondary immunogenicity endpoint data are available and received by the SDCC. Any available data from the exploratory immunogenicity endpoints may also be included in the addendum. Remaining exploratory immunogenicity endpoint data may be included in a further addendum to the CSR, publication of manuscript(s), or other report(s). Abbreviated analysis plans that describe planned analyses to facilitate dissemination of study data for public health reasons, including manuscript publication(s), will be developed by the SDCC. A full statistical analysis plan (SAP) will be developed by the SDCC and finalized prior to the final data lock.

### **12.11.5 General Approach**

Unless otherwise noted in the SAP, continuous variables will be summarized using the following descriptive statistics: n (non-missing sample size), mean, standard deviation, median, maximum and minimum. The frequency and percentages (based on the non-missing sample size) of observed levels will be reported for all categorical measures.

### **12.11.6 Analysis of the Primary Endpoint(s)**

Section 12.11.8 describes the analyses of Safety which is the primary endpoint of this substudy.

### **12.11.7 Analysis of the Secondary Endpoint(s)**

Summaries and analysis of immunogenicity data will be presented for the mITT population. If there are protocol deviations which may affect the analysis, a per-protocol (PP) analysis may also be performed.

GMFR and seroconversion analyses will be done using two definitions of baseline. Baseline 1 will be considered Main Study Day 1 prior to the first mRNA-1273 vaccination (pre-first mRNA-1273 dose baseline) and baseline 2 will be considered Substudy Day 1 prior to the third mRNA-1273 vaccination (pre-third mRNA-1273 dose baseline).

Seroconversion is defined as a 4-fold increase in antibody titer over baseline.

Seroconversion rates, GMFR and GMT for SARS-CoV-2 as measured by IgG ELISA will be calculated at Substudy Days 1, 8, 15, 29, 91, 181 and 366 post third mRNA-1273 vaccination by cohort and will be summarized graphically. Seroconversion rates, GMFR and GMT will be presented with their corresponding 95% confidence interval (CI) estimates at each post-vaccination timepoint and overall peak GMT.

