### 9.4.3 Analysis of the Secondary Endpoint(s)

Summaries and analysis of immunogenicity data will be presented for the mITT population. If there are protocol deviations which may affect the analysis, a per-protocol (PP) analysis may also be performed.

Seroconversion is defined as a 4-fold increase in antibody titer over baseline.

Seroconversion rates, GMFR and GMT for SARS-CoV-2 as measured by IgG ELISA will be calculated at Days 1 (GMT only) and 57 by cohort and will be summarized graphically. Seroconversion rates, GMFR and GMT will be presented with their corresponding 95% confidence interval (CI) estimates at each timepoint and overall peak GMT, and the pair-wise differences between seroconversion rates by cohort will be summarized by study day along with 95% CIs.

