## 12. APPENDIX A: OPTIONAL THIRD mRNA-1273 VACCINATION SUBSTUDY

All aspects of the main study apply to this substudy unless otherwise specified in [Section 12, Appendix A](#).

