## 12.4 Objectives and Endpoints

**Table 12: Objectives and Endpoints (Outcome Measures)**

OBJECTIVES	ENDPOINTS (OUTCOME MEASURES)
Primary	

 
To evaluate the safety and reactogenicity of a third mRNA-1273 vaccination, at a dosage of 100 mcg.
 
	
 
Frequency and grade of each solicited local and systemic reactogenicity AE during a 7-day follow-up period post third mRNA-1273 vaccination.
 
Frequency and grade of any unsolicited AEs during the 28-day follow-up period post third mRNA-1273 vaccination.
 
Frequency of any SAEs, Protocol Specified AESIs, NOCMCs, and MAAEs from Substudy Day 1 to Substudy Day 366.
 

Secondary	

OBJECTIVES	ENDPOINTS (OUTCOME MEASURES)

 
To evaluate the immunogenicity as measured by IgG ELISA to the SARS-CoV-2 S (spike) protein following a third mRNA-1273 vaccination, at a dosage of 100 mcg, at all timepoints after the third mRNA-1273 vaccination.
 
	
 
GMT of antibody at each timepoint after the third mRNA-1273 vaccination.
 
Percentage of subjects who seroconverted, defined as a 4-fold change in antibody titer from the pre-third mRNA-1273 dose baseline (Substudy Day 1) at each post-vaccination timepoint and pre-first mRNA-1273 dose baseline (Main Study Day 1).
 
The GMFR in IgG titer from the pre-third mRNA-1273 dose baseline (Substudy Day 1) at each post-vaccination timepoint and pre-first mRNA-1273 dose baseline (Main Study Day 1).
 

Exploratory	

 
To evaluate the immunogenicity as measured by pseudovirus neutralization and other viral neutralization assays following a third mRNA-1273 vaccination, at a dosage of 100 mcg.
 
	
 
GMT of Neut antibody at each timepoint after the third mRNA-1273 vaccination.
 
Percentage of subjects who seroconverted, defined as a 4-fold change in Neut antibody titer from the pre-third mRNA-1273 dose baseline (Substudy Day 1) at each post-vaccination timepoint and pre-first mRNA-1273 dose baseline (Main Study Day 1).
 
The GMFR Neut antibody titer from the pre-third mRNA-1273 dose baseline (Substudy Day 1) at each post-vaccination timepoint and pre-first mRNA-1273 dose baseline (Main Study Day 1).
 

OBJECTIVES	ENDPOINTS (OUTCOME MEASURES)

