Subjects who receive the third mRNA-1273 vaccination will exit the Schedule of Activities for the main study and will enter the Schedule of Activities for the optional third mRNA-1273 vaccination substudy (see [Table 14](#)). Substudy follow-up visits will occur 1, 2 and 4 weeks post the third mRNA-1273 vaccination (Substudy Days 8, 15, and 29), as well as 3, 6 and 12 months after the third mRNA-1273 vaccination (Substudy Days 91, 181 and 366). Blood will be drawn at these substudy visits for immunogenicity assays. As with prior mRNA-1273 vaccinations, reactogenicity will be measured by the occurrence of solicited injection site and systemic reactions from the time of the third mRNA-1273 vaccination through 7 days after the third mRNA-1273 vaccination. Unsolicited non-serious AEs will be collected from the time of the third mRNA-1273 vaccination through 28 days after the third mRNA-1273 vaccination. SAEs, Protocol Specified AESIs, MAAEs, and NOCMCs will be collected from the time of first mRNA-1273 vaccination through 12 months after the third mRNA-1273 vaccination.

Subjects who do not participate in this substudy, including those who are not eligible to participate in the substudy due to their prior receipt of an FDA authorized (under an EUA) or approved COVID-19 vaccine outside of this clinical trial, will continue, with their permission, to be followed according to the Schedule of Activities for the main study (see [Table 4](#)).

Interim safety and immunogenicity data from this substudy may be reviewed as needed, at the discretion of the study team, to inform public health decisions and to assess the adequacy of the immune responses in the 25 and 50 mcg dose cohorts compared with the 100 mcg dose cohort. Information from interim data reviews may be disseminated to public health officials and partners as needed and included in publications and presentations to inform the global scientific community.

Evaluation of immunogenicity will include quantitation of antibodies to the SARS-CoV-2 S protein at multiple timepoints post third mRNA-1273 vaccination as measured by ELISA and virus neutralization assays. In addition, exploratory studies to characterize T cell responses are planned.

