### **12.11.13 Exploratory Analyses**

Summaries and analysis of immunogenicity data will be presented for the mITT population. If there are protocol deviations which may affect the analysis, a PP analysis may also be performed.

GMFR and seroconversion analyses will be done using two definitions of baseline. Baseline 1 will be considered Main Study Day 1 prior to the first mRNA-1273 vaccination (pre-first mRNA-1273 dose baseline) and baseline 2 will be considered Substudy Day 1 prior to the third mRNA-1273 vaccination (pre-third mRNA-1273 dose baseline).

Seroconversion is defined as a 4-fold increase in antibody titer over baseline.

Seroconversion rates, GMFR and GMT for SARS-CoV-2 as measured by IgG ELISA, neutralization assay using SARS-CoV-2 pseudovirus, neutralization assay using live SARS-CoV-2, and multiplex assay IgG ELISA to the SARS-CoV-2 S proteins and SARS-CoV-2 N protein will be calculated for all post third mRNA-1273 timepoints by cohort and will be summarized graphically. Seroconversion rates, GMFR and GMT will be presented with their corresponding 95% CI estimates at each post-vaccination timepoint and overall peak GMT.

Summaries and analysis of cellular assay data will be presented for the mITT population. If there are protocol deviations which may affect the analysis, a PP analysis may also be performed.

The magnitude, phenotype and percentage of cytokine producing S protein-specific T cells will be summarized at each post-vaccination timepoint by vaccination group.

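### The substudy means to judge 25 and 50 mcg third-dose responses against 100 mcg, but its plan produces no between-dose estimate; a pooled GMT ratio would supply one cheaply

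*Protocol*

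**What the plan says.** Two places in Appendix A of the protocol state the comparison. Section 12.5, in the text after Table 13, allows interim data to be reviewed "to assess the adequacy of the immune responses in the 25 and 50 mcg dose cohorts compared with the 100 mcg dose cohort". Section 12.7.2 attaches a consequence: if responses "in either or both of those cohorts are judged to be suboptimal in comparison to the responses in the 100 mcg cohorts", the team will inform subjects and consider an amendment.

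The analysis is in section 12.11.7. Seroconversion, GMFR and GMT for IgG "will be calculated at Substudy Days 1, 8, 15, 29, 91, 181 and 366 post third mRNA-1273 vaccination by cohort", each with its own 95% CI. It adds that "GMFR and seroconversion analyses will be done using two definitions of baseline", namely Main Study Day 1 and Substudy Day 1. Section 12.11.13 does the same for the exploratory assays; its statistics "will be presented with their corresponding 95% CI estimates at each post-vaccination timepoint and overall peak GMT". Table 12 lists "GMT of antibody at each timepoint after the third mRNA-1273 vaccination" as a secondary endpoint.

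The main study has one between-cohort contrast. In section 9.4.3, "the pair-wise differences between seroconversion rates by cohort will be summarized by study day along with 95% CIs". Appendix A opens with a carry-over rule: "All aspects of the main study apply to this substudy unless otherwise specified". Section 12.11.7 follows the wording of 9.4.3 but leaves out the pair-wise clause.

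**The concern.** A stated comparison with a stated consequence should have an estimate behind it. Here the reader of the output gets three age-specific GMTs per prior dose, each from 10 to 15 subjects at most, with separate intervals. Nothing combines them into a 25 vs 100 or 50 vs 100 mcg figure with its own interval.

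Nor does anything say which measure or visit counts. For IgG alone there are 5 measures (GMT, plus GMFR and seroconversion on two baselines), 6 post-dose visits, 3 age strata and 2 dose contrasts: 5 x 6 x 3 x 2 = 180 possible informal comparisons. In an open-label study with discretionary looks, the basis for calling a response suboptimal could be chosen after the data are seen.

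One of those measures is a poor basis when used alone. A 4-fold rise from Substudy Day 1 depends on the titer at which the subject starts. Section 12.2 reports that antibody responses were dose-dependent and declined after the second dose, so starting titers may differ by prior dose.

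**Working it through.** **The plan's own figures.** No sample size or precision is given for any immunogenicity comparison. The figures in section 12.11.2 concern adverse events, and they reproduce: 1 - 0.8^5 = 67.2% (stated as about 67%) and 1 - 0.97^120 = 97.4% (stated as about 97%).

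**Eligible numbers.** Table 13 gives 15 + 10 + 10 = 35 per prior dose for 25, 50 and 100 mcg. Its footnote says that two subjects in cohort 1 and one in cohort 5 missed the second dose. This leaves 33 (25 mcg), 35 (50 mcg) and 34 (100 mcg).

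**Precision of a GMT ratio.** The documents give no SD for log10 titer; 0.3 to 0.5 is assumed. The 95% CI is the ratio multiplied and divided by F = 10^(t x SD x sqrt(1/n1 + 1/n2)). The pooled model has one dose term and two age terms, so df = n1 + n2 - 4; for single cohorts, df = n1 + n2 - 2.

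Example, 33 vs 34 at SD 0.4: t(63) = 1.998 and sqrt(1/33 + 1/34) = 0.2444, so F = 10^(1.998 x 0.4 x 0.2444) = 10^0.195 = 1.57.

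| Comparison | F, SD 0.3 | F, SD 0.4 | F, SD 0.5 |
|---|---|---|---|
| Pooled over age, full uptake, 33 vs 34 | 1.40 | 1.57 | 1.75 |
| Single cohorts, 10 vs 10 | 1.91 | 2.38 | 2.95 |
| Pooled over age, 5 per cohort, 15 vs 15 | 1.68 | 2.00 | 2.37 |
| Single cohorts, 5 vs 5 | 2.74 | 3.83 | 5.36 |

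The 5-per-cohort rows use the uptake considered in section 12.11.2. The 50 vs 100 mcg contrast (35 vs 34) is almost the same as the first row: 1.39, 1.56 and 1.74.

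**If the pair-wise seroconversion difference did carry over.** For 8/10 vs 8/10 its 95% CI (Newcombe) runs from -34 to +34 percentage points.

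**Why 4-fold rise from Substudy Day 1 should not stand alone.** Take log10 rise as normal, so that the rate is Phi((log10 GMFR - log10 4)/SD). Give two groups the same post-dose titers, but let one start 2-fold lower, which doubles its GMFR. Both the 2-fold difference and an SD of 0.4 (range 0.3 to 0.5) are assumed.

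| GMFR, lower start vs higher start | Rates at SD 0.4 | Difference in points (SD 0.3 to 0.5) |
|---|---|---|
| 8 vs 4 | 77% vs 50% | 27 (23 to 34) |
| 16 vs 8 | 93% vs 77% | 16 (14 to 16) |
| 32 vs 16 | 99% vs 93% | 5 (2 to 8) |

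The difference comes only from the starting titer and shrinks as fold rises grow. The GMT ratio in the same example is 1.

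**The case against.** The strongest reply is that nothing is missing except a presentation line. GMTs by cohort, with intervals, are planned at every post-dose visit, and they do not depend on the Substudy Day 1 titer. Anyone making the section 12.7.2 judgement will see them, can divide two of them and can approximate an interval. The comparison is not a listed objective, the review is at the team's discretion, section 12.11.1 disclaims any hypothesis, and the consequence is only to inform subjects and consider an amendment. Section 12.11.4 also promises abbreviated analysis plans and a substudy SAP. The supplied SAP lists only the two-dose objectives, so its silence on the substudy shows nothing.

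Most of this stands, and it sets the weight of the point. It does not remove it. Separate cohort intervals do not give an age-pooled dose ratio, and the substudy SAP is due only before final lock, which can be after the reviews that use the comparison.

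A reader might also infer that the plan rests the judgement on a biased measure, 4-fold rise from Substudy Day 1. The documents do not support that. No section ties the judgement to that measure, and since 12.11.7 restates the analysis without the pair-wise clause, the main-study contrast may well not apply.

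A reader might likewise infer that prior dose and dosing interval are confounded by design. Section 12.5 offers the third dose to the 25 and 50 mcg cohorts soon after Day 209 and lets the 100 mcg cohorts receive it up to the close of the Day 394 window. It permits a longer interval for 100 mcg but does not require one. The net effect on fold rise has no known direction: a higher prior dose would raise the starting titer and a longer interval would lower it.

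**Conclusion.** The point holds as a gap between a stated question and the planned output. Sections 12.5 and 12.7.2 call for a 25/50 vs 100 mcg comparison, and sections 12.11.7 and 12.11.13 produce no estimate or interval for it. It is a worthwhile, low-cost improvement in a descriptive substudy, not a mistake in an analysis that is planned.

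The gain is a CI factor of about 1.4 to 1.8 for the pooled ratio at full uptake, against 1.9 to 3.0 for two cohorts of 10. These figures rest on an assumed log10 SD of 0.3 to 0.5 and, for pooling, on a dose ratio that is similar across age strata. They widen with lower uptake, to about 1.7 to 2.4 pooled at 5 per cohort. The starting-titer figures show only why one measure should not be used alone; they do not estimate a bias in this substudy.

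**What to change.** In section 12.11.7, or in an abbreviated analysis plan under section 12.11.4 finalized before any adequacy review:

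- Add the ratio of post-third-dose IgG GMT, 25 vs 100 and 50 vs 100 mcg, at one named visit such as Substudy Day 29, pooled over and adjusted for age stratum, with 95% CI.
- Tabulate the dose 2 to dose 3 interval and the Substudy Day 1 titer by cohort.
- Keep GMFR and 4-fold rise as planned, but do not base the comparison on 4-fold rise from Substudy Day 1 alone.
- State whether the pair-wise differences of section 9.4.3 apply to the substudy.

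An interval-adjusted analysis is an optional sensitivity check.

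The cost is some wording, a descriptive table and one simple model on data already collected, with no change to visits or dosing. The limit is that the ratio cannot separate prior dose from interval if timing turns out to differ by dose; the table would show whether it does. No threshold, dose or clinical rule is proposed.
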